#### **6.15.3 Vital Signs, Height and Weight, and Other Safety Measures**

Vital signs will be summarized by presenting summary statistics of raw data and change from baseline values (means, medians, standard deviations, ranges) for each visit (per analysis window) and time point. A data listing will include vital signs from all visits.

#### **6.15.4 Electrocardiogram**

Incidence of the Investigator's overall assessment (normal, abnormal – not clinically significant, and abnormal – clinically significant) will be summarized.

#### **6.15.5 Physical Examination**

New or worsening symptoms in the symptom-directed physical exams will be included in the by-subject data listing.

#### **6.15.6 Analysis of Anti-Drug Antibody**

A data listing of anti-drug-antibodies (ADA) results will be provided for all subjects. Number (%) of subjects who are confirmed ADA-positive at any time after receiving study drug and number (%) of subjects who are confirmed ADA-positive at the end of study will be cross-tabulated by their ADA status and titers at predose.

### **7. Validation**

The Clinical Operations and Data Management at Allakos will work with the EDC/Data Management (DM) vendor to ensure that the data collected for the study are of the highest quality possible. The study monitor will be responsible for reviewing and verifying the accuracy of the data recorded on the eCRF directly from source documents at the investigative site. The DM vendor will be responsible for performing edit checks and reviewing all data entered into the electronic database to identify discrepant and/or inconsistent values and to send queries to the clinical sites. The Investigator will be responsible for answering queries about discrepant data and providing electronic signatures to confirm data integrity.

The programming of tables, listings and figures (TLF) based on the clinical data is outsourced. Allakos seeks to ensure the quality of the reports provided by the CRO in the form of TLF passing a rigorous validation process as follows:

- Derived datasets will be independently reprogrammed by a second programmer. The separate datasets produced by the 2 programmers must match 100%.
- Tables will be independently reprogrammed by a second programmer, and the results from both programs must match.
- Figures will be checked for consistency against corresponding tables and listings or independently reprogrammed if there are no corresponding tables or listings.
- Listings will be checked for consistency against corresponding tables, figures, and derived datasets.

All post hoc analysis, if accepted for inclusion in the study report, will follow the same quality process as stated above. The entire set of TLF will be checked for completeness and consistency prior to delivery to Allakos.

## 9.1 Appendix 1: Effect of Missing Data on the Weekly Mean of TSS

Following the FDA's suggestion for the evaluation of the missing daily diary effect on the weekly mean of TSS score, data from the Phase 2 study are extracted. The Phase 2 study has diaries collected daily over 14 weeks of the treatment period. A simulation study was conducted examining the changes in standard error by the number of missing daily diaries that were randomly created. The steps are as follows.

- 1) A complete data set is created in which a subject week is kept only if the week has all 7 daily diaries. This data set is at the subject-day level.
- 2) For each week in the complete data set, 1 of the 7 daily diaries is randomly set to missing. This creates a data set with 1 day per week missing.
- 3) Step 2 is repeated for 2 of the 7 daily diaries are randomly set to missing to create a data set with 2 days per week missing.

Finally, a data set is created with 6 days per week are randomly set to missing.

- 4) For each of the 7 data sets (0 day/week missing, 1 day/week missing, ..., 6 days/week missing), daily diaries are averaged to derive the weekly mean for each subject at each week.
- 5) Weekly means of the diaries are further averaged across all subjects to derive the population means and population standard error of the diaries for each week.
- 6) Steps 2 through 5 are repeated 500 times. Each time, the daily diaries are randomly set to missing.
- 7) The 500 weekly population standard errors from Step 6 are averaged and presented in the table below.

As expected, the standard error increases as the number of missing daily diaries increases, indicating the estimate of weekly TSS mean becomes less accurate. However, the increase in the standard error does not exceed 2% when allowing 3 out of 7 daily diaries missing, and does not exceed 4% when allowing 4 out of 7 daily diaries missing.

**Table 7 Standard Errors for the Mean Weekly TSS Diaries by Number of Daily Diaries Missing Averaged over 500 Simulations**

Week	Number of Daily Diaries Missing						
	0 Day	1 Day	2 Days	3 Days	4 Days	5 Days	6 Days
1	3.092	3.100	3.115	3.132	3.166	3.232	3.405
2	2.917	2.923	2.929	2.941	2.964	3.003	3.102
3	3.070	3.081	3.088	3.095	3.125	3.198	3.321
4	2.862	2.868	2.874	2.881	2.894	2.926	2.994
5	3.111	3.118	3.122	3.134	3.149	3.187	3.293
6	3.135	3.137	3.147	3.154	3.170	3.191	3.279
7	3.039	3.045	3.054	3.067	3.093	3.140	3.283
8	3.842	3.846	3.849	3.858	3.871	3.884	3.959
9	2.854	2.869	2.874	2.899	2.932	3.021	3.176
10	2.823	2.829	2.840	2.845	2.857	2.886	3.010
11	2.997	3.002	3.010	3.008	3.037	3.069	3.148
12	2.656	2.661	2.671	2.689	2.691	2.731	2.842
13	2.864	2.879	2.886	2.905	2.950	3.011	3.208
14	2.388	2.402	2.414	2.437	2.474	2.580	2.795

Source: K:\AK002-016\planning\MissingOnSE.sas 08MAR2020

## 9.2 Appendix 2: Intercurrent Events

A. Use of any of the following prohibited medications during the course of the study as described

- 1) Immunosuppressive or immunomodulatory drugs (e.g., IL-5 modulators, i.e., benralizumab, reslizumab, mepolizumab; IL-4 and IL-13 antagonists, i.e., dupilumab; calcineurin inhibitors, i.e., cyclosporin, tacrolimus; mTOR inhibitors, i.e., sirolimus, everolimus; anti-metabolites, i.e., azathioprine, methotrexate, 6-mercaptopurine, leflunomide, mycophenolate mofetil; alkylating agents, i.e., cyclophosphamide; TNF inhibitors, i.e., infliximab, adalimumab; anti-IgE antibodies, i.e., omalizumab; and eosinophil-depleting drugs, i.e., pramipexole.
  - a) Use at any point during the study.
- 2) Glucocorticoids
  - a) Initiation of any course of treatment or single use of systemic or swallowed corticosteroids at a dose of  $>10$  mg/day prednisone or equivalent starting at Week 21 and through the end of Week 24. This does not include use of corticosteroids given as pre-infusion prophylaxis or treatment of IRR.

B. Use of restricted medications outside the protocol-defined specifications

- 1) Glucocorticoids
  - a) Discontinuation of a previously stable dose of systemic or swallowed corticosteroids ( $\leq 10$  mg/day prednisone or equivalent) after the screening period.
  - b) Initiation of a new course of systemic or swallowed corticosteroids ( $\leq 10$  mg/day prednisone or equivalent) following the screening period and continuing to at least study Week 21 (within 2 weeks of efficacy assessment at Weeks 23 and 24).
- 2) Proton Pump Inhibitors
  - a) Discontinuation of a previously stable dose of an oral PPI after the screening period and before the end of Week 24.
  - b) Initiation or increase in the dose of an oral PPI following the screening period and continuing to at least study Week 21 (within 2 weeks of efficacy assessment at Weeks 23 and 24).
- 3) Sodium cromolyn
  - a) Discontinuation of a previously stable dose of sodium cromolyn after the screening period and before the end of Week 24

- b) Initiation or increase in the dose of sodium cromolyn following the screening period and continuing to at least study Week 22 (within 1 week of efficacy assessment at Weeks 23 and 24).

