15.6 Efficacy Analysis

15.6.1 Primary Efficacy Endpoint Analysis

The first co-primary endpoint will be analyzed using Fisher's exact test. Patients who experience an ICE, i.e., exit the study prematurely or initiate prohibited or restricted medication, prior to end of Week 24 will be treated as non-responders. Proportion of responders and the associated 95% confidence interval (CI) will be presented for each treatment group. The between-group difference and the associated 95% CI will also be computed and presented. Sensitivity analysis may be carried out using the Cochran-Mantel-Haenszel (CMH) test stratified by the randomization stratification factor (baseline TSS <28 vs ≥ 28) to assess robustness of Fisher's exact test results.

The rationale for specifying Fisher's exact test for the primary analysis as opposed to specifying the CMH test is because when a stratum has 100% response for 1 treatment group and 0% response for another treatment group, the CMH test may lose efficiency or not be computable. This is evident from the Phase 2 study outcome.

The second co-primary endpoint will be analyzed using mixed model for repeat measures (MMRM) with treatment, week, treatment-by-week interaction, and baseline TSS-by-week interaction as fixed factors; gender and baseline TSS (continuous) as covariates; and study site (with pooling by geographic location) as random effect. If the model does not converge with pooled sites as a random effect, it will be simplified with pooled site as a fixed effect. Details about the method for pooling sites will be provided in the statistical analysis plan (SAP).

The weekly TSS is calculated as the average of the daily TSS. Weekly TSS will be set to missing if >3 daily TSS are missing. Baseline TSS will be the average of the last 2 weeks of daily TSS collected prior to the first infusion. The model variance-covariance matrix will be unstructured. However, if computation does not converge, the matrix will take the form of Toeplitz, autoregressive, or compound symmetry, whichever converges first.

Data on patients who experience an ICE, i.e., exit the study prematurely or initiate prohibited or restricted medications, prior to the end of Week 24 will be set to missing. If it is evident that the

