**Table 2 Terminology and Definitions cont.**

Terminology	Definition
Patient-Reported Outcome cont.	
 
• Diarrhea intensity
 
• Diarrhea frequency
 
• Fullness before finishing a meal (Early satiety) intensity
 
• Loss of appetite intensity
 
• Bloating intensity
 
• Abdominal cramping intensity
 

	Each intensity evaluation is scored on a scale of 0=none to 10=worst possible.
Prior Medication	Medication collected on the Prior/Concomitant Medication CRF, with start date prior to Study Day 1.
PRO Total Symptom Score	Total symptom score (TSS) is the sum of 6 (abdominal pain, abdominal cramping, bloating, nausea, early satiety, and loss of appetite) weekly average symptom intensity scores.
Study Day	Study Day 1 is defined as the date on which a subject took the first dose of study drug. Other study days are defined relative to Study Day 1. For visits prior to the first dose of study drug, Study Day is calculated as Visit Date – Day 1 Date. For visits after the first dose, Study Day is calculated as Visit Date – Day 1 Date +1.
Study Drug	AK002 or placebo administered by IV infusion.
Study Week	Study Week for PRO analysis is defined as 7 days a week starting from the day of first dose (Day 1).
Tissue Eosinophil Responder in EoD	Mean duodenal eosinophil count $\leq$ 15 cells/hpf in 3 highest duodenal hpf.
Treatment-emergent	Adverse events reported in the clinical database with a date of onset on or after the start date of the first dose of the study drug.
Treatment Responder	Subject with >30% improvement in TSS from baseline and mean eosinophil count $\leq$ 15 cells/hpf in 3 highest duodenal hpf.

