#### **4.2.5 Strategy for Handling Intercurrent Events**

For the analysis of the study product estimand, tissue eosinophil values and TSS will be counted as non-responders for binary variables and set to missing for continuous outcomes from the point when an ICE occurs. The estimand will provide an answer to the question that is crucial to individual subjects:

“If I take this study medication as part of my treatment regimen, without adding any further medications that may impact the underlying disease or exit the study prematurely, what improvements in histology and PRO symptoms might be anticipated after 24 weeks?”

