### 5.4 Handling of Dropouts, Missing Data, and Data Discrepancies

#### 5.4.1 Missing Duodenal Tissue Eosinophil Count at Week 24

Eosinophil counts will be set to missing if they are collected after subjects have experienced ICE. Subject with missing Week 24 tissue eosinophil count for any reason will be imputed with the eosinophil count collected from the postbaseline unscheduled visit prior to missing. If no eosinophil count is collected postbaseline, the subject will be considered treatment failure for tissue eosinophil response.

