#### C. Discontinuation of Investigational Medical Product

- 1) Discontinuation of study agent due to:
  - a) Infusion-related reaction
  - b) Subject withdrawal
  - c) Meeting study withdrawal criteria (Protocol Section 13.10)

Per protocol, subjects are required to remain on stable doses of either PPI or corticosteroids ( $\leq 10$  mg prednisone equivalent per day) throughout the course of the study if they are on a stable dose during the screening period. Because of the potential impact of corticosteroids and PPI on both histologic assessment of tissue eosinophil levels as well as subject reported GI symptoms, subjects must meet the entry requirements for both histology and symptom burden (TSS6) if they are on any of these medications at screening and therefore must remain on a stable dose throughout the study in order to meaningfully interpret any change from baseline during the evaluation phase. Conversely, subjects starting these medications due to unforeseen medical necessity following the screening period and remaining on them through a time point sufficiently close to the evaluation period to potentially impact assessment of symptoms and/or histologic assessments will be considered as intercurrent events. For PPI and corticosteroids ( $\leq 10$  mg/day prednisone or equivalent) a conservative washout period is estimated at 2 weeks, and therefore, continuation of a new course of therapy beyond Week 21 could be considered as a potential ICE.

Sodium cromolyn is a mast cell stabilizer and could potentially impact reported symptoms in a similar way to 1 of the mechanisms of action of AK002. As such, discontinuation of a previously stable dose of sodium cromolyn after the screening period and before the end of Week 24 could be considered as a potential ICE. Likewise, the initiation or increase in the dose of sodium cromolyn following the screening period and continuing to at least study Week 22 (within 1 week of efficacy assessment at Weeks 23 and 24) could be considered as a potential ICE. It is estimated that 1 week would be a sufficient washout period for the effects of sodium cromolyn.

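### SAP Appendix 2 does not list as an intercurrent event a steroid course above 10 mg/day that starts before Week 21 and is still running at the endpoint, although a lower-dose course with the same dates is listed

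*SAP*

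**What the plan says.** SAP 4.2.4 names two ICEs, early exit from the study and use of prohibited or restricted medication, and sends the detail to Appendix 2. The steroid items there are:

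- **A.2.a (above 10 mg/day).** Initiation of a course, or a single use, at >10 "mg/day prednisone or equivalent starting at Week 21 and through the end of Week 24". Pre-infusion prophylaxis and treatment of infusion reactions are exempt.
- **B.1.a (10 mg/day or less).** Stopping a stable dose after screening.
- **B.1.b (10 mg/day or less).** A new course at ≤10 "mg/day prednisone or equivalent) following the screening period and continuing to at least study Week 21".

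The proton pump inhibitor (PPI) item is broader in kind: "Initiation or increase in the dose of an oral PPI following the screening period and continuing to at least study Week 21". The sodium cromolyn item also covers increases.

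The narrative that closes Appendix 2 says steroids and PPIs can affect both histology and symptoms. It adds that patients who start such drugs after screening and stay on them close enough to the "evaluation period to potentially impact assessment of symptoms and/or histologic assessments will be considered as intercurrent events". Its two-week washout and Week 21 cut-off are given only for PPIs and for steroids at or below 10 mg/day.

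The estimand question in SAP 4.2.5 asks what a patient may expect "without adding any further medications that may impact the underlying disease or exit the study prematurely". Protocol 15.6.1 says that, for the histology endpoint, patients who "exit the study prematurely or initiate prohibited or restricted medication, prior to end of Week 24 will be treated as non-responders".

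ICE status decides which data are used. SAP 5.4.1 states: "Eosinophil counts will be set to missing if they are collected after subjects have experienced ICE". SAP 5.4.2 does the same for daily symptom scores.

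**The concern.** The two steroid items use different tests. The low-dose item asks whether the course reaches Week 21; the high-dose item asks only whether it began in Weeks 21–24. A course above 10 mg/day that began earlier and is still running meets neither. An increase from a stable low dose to above 10 mg/day before Week 21 is not listed either. The list is therefore more lenient to the larger exposure, which is hard to square with the estimand or the narrative.

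The case can arise. Protocol 8.2 treats steroids above 10 mg/day for EoD, at any time in the study, as rescue and lets the patient remain.

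At stake is whether outcomes measured on such steroids count as valid in both co-primary analyses. If steroids improve those outcomes, their use on placebo shrinks the apparent treatment effect and their use on AK002 enlarges it. If the gap is found only after unblinding, either reading can be disputed.

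**Working it through.** **1. Dates.** SAP Table 2 counts study weeks as seven-day blocks from Day 1, so Week w covers Days 7(w−1)+1 to 7w.

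- Week 20 ends on Day 140.
- Week 21 is Days 141–147.
- Weeks 23–24 are Days 155–168.

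**2. The items applied literally.**

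| Course | Dates | Item met |
|---|---|---|
| New, ≤10 mg/day | Day 140 to 168 | B.1.b: ICE |
| New, >10 mg/day | Day 140 to 168 | none |
| New, >10 mg/day | Day 141 to 168 | A.2.a: ICE |
| Increase to >10 mg/day | Day 140 to 168 | none |

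A start one day earlier removes ICE status at the higher dose but not at the lower. A.2.a does not reach start dates in 20 of the 24 weeks (140/168 = 83% of days), although the gap matters only when the course also runs to Week 21 or later.

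**3. Does other text fill the gap?** SAP 4.2.4 is general and defers to Appendix 2. Protocol 4.5.4 defers to the SAP, and SAP Section 1 says the SAP supersedes the protocol's statistical methods. Item A.1 (immunosuppressants) cannot absorb steroids, which have their own item and window.

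**4. Possible effect on the TSS test.** Inputs from the sample-size sections (Protocol 15.1, SAP 3.5): difference 7.4, SD 12.5, 40 per arm, two-sided alpha 0.05. A two-sample t-test without covariates gives power 0.744, against the stated 80%; 0.744 is the reference below.

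The documents give neither the number of affected patients (k) nor the steroid gain in TSS (g), so both are assumed: k = 1, 2 or 4 placebo patients and g = 4, 8 or 16.07. The upper bound is the mean placebo TSS remaining in AK002-016 (Protocol Table 1): 27.57 − 11.5 = 16.07.

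- Data kept: difference = 7.4 − g·k/40, with 40 per arm.
- Set to missing: difference 7.4, with 40 versus 40 − k.

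| k | Difference if kept (g = 4 / 8 / 16.07) | Power if kept | Power if set to missing |
|---|---|---|---|
| 1 | 7.30 / 7.20 / 7.00 | 0.732 / 0.720 / 0.696 | 0.738 |
| 2 | 7.20 / 7.00 / 6.60 | 0.720 / 0.696 / 0.645 | 0.732 |
| 4 | 7.00 / 6.60 / 5.79 | 0.696 / 0.645 / 0.535 | 0.720 |

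Keeping the data rather than setting them to missing costs 0.6 to 4.2 percentage points for one patient and 2.4 to 18.5 for four. If the affected patients are on AK002 instead, the difference is inflated by g·k/40, that is 0.1 (4·1/40) to 1.6 (16.07·4/40) points.

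**5. Possible effect on the histology test.** Planned rates are 0.60 and 0.10. If every affected placebo patient counts as a responder, the placebo rate is 0.10 + 0.90·k/40 = 0.1225, 0.145 or 0.19. Fisher power is then 0.995, 0.988 or 0.958.

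**The case against.** The strongest reply is that the course is not truly unclassified. SAP 4.2.4 and Protocol 15.6.1 would both make it an ICE on their general wording. The narrative's sentence on patients starting these drugs can be read without a dose limit, and a course covering all of Days 155–168 needs no washout figure to fall under it. Stepping up to above 10 mg/day might also count as initiating a course at that dose, or as stopping a stable one under B.1.a.

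This shows that the documents conflict, not that the list works. The general statements defer to Appendix 2, and the low-dose limit stands in the sentences on either side of the narrative's rule. The readings for increases are possible but not written, and the PPI and cromolyn items show that the authors named increases when they meant them.

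On size, much of the reply stands. Protocol 8.2 confines this use to necessity and asks for early discontinuation, so cases may be few. The 16-point gain supposes that an average placebo patient reaches a TSS of zero. The direction also depends on who is rescued: placebo patients who would otherwise have been 8 points worse than average and gain 8 leave the difference at 7.4, and if they gain only 4 it rises to 7.5 for one patient or 7.8 for four. A per-protocol MMRM and a listing of ICEs are planned, but the listing would not show a course that is not classified as an ICE, and the per-protocol analysis is supplementary.

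It is also fair that no washout is given above 10 mg/day. Week 21 is, however, the boundary A.2.a already uses.

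**Conclusion.** The concern holds. The operative list leaves out a steroid course above 10 mg/day, new or increased, that starts after screening and before Week 21 and is still running at Week 21 or later. It lists a new course at or below 10 mg/day with the same dates. Under SAP 5.4.1 and 5.4.2 the omitted patient's data stay in both co-primary analyses, contrary to SAP 4.2.5 and Protocol 15.6.1. A SAP list narrower than the protocol is not in itself an error, since the protocol leaves the detail to the SAP; the error is the reversal by dose.

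The consequence falls on the TSS endpoint. Its size is illustrative only, because it rests on assumed counts and gains and on affected patients being otherwise average. Histology power stays at or above 95.8% in every case tried. This should be fixed before unblinding.

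**What to change.** Before unblinding, reconcile A.2.a with B.1.b, the Appendix 2 narrative and Protocol 15.6.1:

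- Keep the present A.2.a trigger. Add that a new or increased course above 10 mg/day, begun at any time after screening and continuing to at least Week 21, is an ICE for analysis. If the sponsor prefers another cut-off, state it with its reason.
- State whether courses above 10 mg/day that end before Week 21 are ICEs. Protocol 15.6.1 would count them; Appendix 2 does not.
- Keep stable baseline use at or below 10 mg/day and all the circumstances in Protocol 8.3 outside the flag. Name the single IV dose at the EGD. Protocol 8.3 already says it is not prohibited, but the exemption in A.2.a does not mention it, and the EGD window (Days 166–172) overlaps Week 24 (to Day 168).

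This changes analysis classification only, not the care patients may receive. The cost is one or two SAP sentences and the matching derivation; a few more patients may become non-responders or have TSS set to missing.

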#### **4.2.4 Intercurrent Events**

The events below are considered intercurrent events (ICE) confounding with the efficacy outcomes.

- Premature discontinuation from the study
- Use of prohibited/restricted medication

Further clarification and handling of ICE including prohibited/rescue medications is detailed in [Appendix 2](#).

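### SAP Appendix 2 does not list a corticosteroid rescue course above 10 mg/day as an intercurrent event if it began before Week 21 and is still running, although a lower-dose course on the same dates is listed

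*SAP*

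**What the plan says.** SAP 4.2.4 names two kinds of intercurrent event (ICE): leaving the study early, and "Use of prohibited/restricted medication". It sends the clarification and handling to Appendix 2. The items there that bear on corticosteroids are:

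- **A.2.a, above 10 mg/day.** A course or single use at a dose above 10 "mg/day prednisone or equivalent starting at Week 21 and through the end of Week 24". The exemption reads: "This does not include use of corticosteroids given as pre-infusion prophylaxis or treatment of IRR".
- **B.1.a, 10 mg/day or less.** Stopping a previously stable dose after screening.
- **B.1.b, 10 mg/day or less.** A new course at up to 10 "mg/day prednisone or equivalent) following the screening period and continuing to at least study Week 21".

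The PPI item, by contrast, is worded "Initiation or increase in the dose of an oral PPI following the screening period and continuing to at least study Week 21", and the cromolyn item also covers dose increases. No glucocorticoid item mentions an increase.

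The narrative closing Appendix 2 cites the "potential impact of corticosteroids and PPI on both histologic assessment of tissue eosinophil levels as well as subject reported GI symptoms". It says that patients who start these drugs after screening, "remaining on them through a time point sufficiently close to the evaluation period to potentially impact assessment of symptoms and/or histologic assessments", will be ICEs. For PPI and for corticosteroids at 10 mg/day or less it adds that "a conservative washout period is estimated at 2 weeks, and therefore, continuation of a new course of therapy beyond Week 21" could be one.

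Protocol 8.2 classes more than 10 mg/day for EoD as rescue whenever it occurs. It limits such use to medical necessity and asks for early discontinuation. It allows the patient to remain in the study and sets no week by which the course must end.

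**The concern.** The carry-over rule, which looks at whether a course is still running close to the efficacy assessment, is attached only to the low dose. The high dose is judged by its start date alone. A patient rescued with high-dose steroid in Week 18 and still taking it at the Week 24 biopsy is therefore outside the list, while a patient on a quarter of the dose over the same dates is inside it. No reason is given for this inversion.

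The consequence follows from SAP 5.4.1 and 5.4.2, which set eosinophil counts and daily PRO scores to missing only after an ICE. If the course is not an ICE, both co-primary endpoints use data collected on high-dose steroid. The estimand question in SAP 4.2.5 and Protocol 4.5.5 asks about the effect when no further medication acting on the underlying disease is added. The patient would also be absent from the ICE listing and the by-arm ICE table in SAP 6.11, which exist to show such use. They would be visible only in the medication tables and listings (SAP 6.10.2), or if excluded from the per-protocol population.

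**Working it through.** **Which item catches which course**

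Inputs: the wording of A.2.a and B.1.b, and SAP Table 2, which counts study weeks as 7 days from Day 1. Week *w* starts on Day 7(*w* − 1) + 1, so Week 21 starts on Day 141, Weeks 23–24 are Days 155–168, and Day 120 falls in Week 18 (Days 120–126).

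The two rules reduce to:

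- A.2.a: dose above 10 mg/day and start in Weeks 21–24.
- B.1.b: dose 10 mg/day or less, started after screening, and still running at Week 21 or later.

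Applied to a new course:

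| Start–end week | Above 10 mg/day | 10 mg/day or less |
|---|---|---|
| 10–14 | none | none |
| 18–20 | none | none |
| 18–21 | none | B.1.b |
| 18–22 | none | B.1.b |
| 18–24 | none | B.1.b |
| 20–24 | none | B.1.b |
| 21–21 | A.2.a | B.1.b |
| 22–24 | A.2.a | B.1.b |

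The two doses part exactly when the course starts before Week 21 and runs to Week 21 or later. For example, a new course from Day 120 to Day 169 is an ICE at 5 mg/day and matches nothing at 20 or 40 mg/day.

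The remaining items do not help. A.1 lists other immunosuppressive and immunomodulatory classes; reading corticosteroids into it would make A.2 redundant. B.1.a concerns stopping a low dose. B.2 and B.3 concern PPI and cromolyn. C concerns stopping study drug.

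**Size on TSS**

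The documents give neither a rescue rate nor a steroid effect on TSS, so the following are assumptions: *k* patients in one arm of 40, each with *b* points of steroid benefit. The shift in that arm's mean is *k* × *b* / 40, compared with the planned difference of 7.4 points (SAP 3.5).

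| *k* | *b* | Shift (points) | Share of 7.4 |
|---|---|---|---|
| 1 | 5 | 5/40 = 0.125 | 1.7% |
| 2 | 10 | 20/40 = 0.50 | 6.8% |
| 4 | 10 | 40/40 = 1.0 | 13.5% |
| 4 | 15 | 60/40 = 1.5 | 20.3% |

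This measures contamination against a steroid-free outcome. It is not the amount by which the MMRM estimate would move if the values were set to missing.

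**Size on histology**

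One patient of 40 is 2.5 percentage points. With AK002 held at the planned 24/40 (0.6), the two-sided Fisher exact test gives:

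| Placebo responders | p |
|---|---|
| 4/40 (planned, 0.1) | <0.0001 |
| 8/40 | 0.0005 |
| 14/40 | 0.043 |
| 15/40 | 0.073 |

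Ten extra placebo responders would still leave the histology test significant.

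**The case against.** The strongest reply is that other text already covers the case. Protocol 15.6.1 treats anyone who initiates prohibited or restricted medication before the end of Week 24 as a non-responder and sets their TSS to missing, and Protocol 8.2 calls this use restricted. SAP 4.2.4 repeats the general category without a time window. The Appendix 2 narrative is part of the appendix; its statement about starting these drugs is mandatory, and the sentence just before it mentions corticosteroids without a dose limit. Section A is also headed by use of the drugs, so a patient taking 40 mg/day during Weeks 21–24 could be said to be using it in the window. Finally, a course tapered to 10 mg/day or less by Week 21 arguably meets B.1.b, and a step-up from a stable low dose arguably meets B.1.a.

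Some of this stands. The intent is clear enough, and the defect is a conflict between the item list and the general text, not silence across both documents. The taper case may well be caught.

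The rest does not close the gap. The SAP states in its Introduction that it supersedes the protocol's statistical methods, and 4.2.4 defers to Appendix 2. The appendix deliberately narrows the general rule: low-dose steroid, PPI and cromolyn courses that end early are not ICEs, so the general category cannot serve as a catch-all. The narrative introduces corticosteroids at 10 mg/day or less and gives its washout only for that dose. A.2.a is worded around initiation and start date. Reading a step-up into an item about discontinuation is strained when the PPI and cromolyn items list discontinuation and increase separately.

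It is also fair that the size is assumed, that Protocol 8.2 restrains such use, and that the 20% figure needs four patients in one arm gaining 15 points each, when mean changes in the earlier Phase 3 study were −10.0 and −11.5 (Protocol Table 1).

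**Conclusion.** The concern holds. As itemised, Appendix 2 omits the carried-over high-dose course and includes the low-dose course on the same dates. Two analysts could classify the same patient differently in both co-primary analyses.

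The number of patients is probably small. Histology significance is robust under the planned rates; TSS is the more exposed endpoint. If steroids improve TSS, more rescue on placebo shrinks the observed difference and more rescue on AK002 inflates it. The 1.7% to 20% range rests on the assumed *k* and *b* and on 40 analysed per arm. The primary analysis uses the Evaluable population, so if that leaves fewer than 40 per arm, each such patient weighs somewhat more. This is worth correcting before unblinding, but nothing here shows that either co-primary conclusion would change.

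**What to change.** Add an item to Appendix 2: any new or increased course of systemic or swallowed corticosteroid above 10 mg/day prednisone equivalent, begun after screening and continuing to Week 21 or later, is an ICE. State its washout, at least as long as the 2 weeks used for the lower dose.

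Name the exemptions in the same item: premedication required by the protocol or approved by the Medical Monitor, treatment of an infusion-related reaction, and the single intravenous dose at EGD. Protocol 8.3 permits that last dose, but the A.2.a exemption omits it. This matters only when the EGD falls within Week 24, for instance on Days 166–168 of the Day 169 ± 3 window.

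Add a corticosteroid-rescue row by arm to the ICE table planned in SAP 6.11.

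The cost is one appendix entry and one row in a table already planned, settled before unblinding. The downside is that a few more patients become histologic non-responders or have TSS set to missing.
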